8.4.6 Spirometry at Screening and Visit 1 Pre-dose

The following spirometry parameters will be summarised by treatment regimen and overall:

- Screening: FEV1 pre- and post-bronchodilator, FEV1 % of predicted normal value pre- and post-bronchodilator, FVC pre- and post-bronchodilator, FVC % of predicted normal value pre- and post-bronchodilator, FEV1/FVC pre- and post-bronchodilator, FEV1/FVC % of predicted normal value pre- and post-bronchodilator
- Visit 1: FEV1 post-bronchodilator, FEV1 % of predicted normal value post-bronchodilator, FVC post-bronchodilator, FVC % of predicted normal value post-bronchodilator, FEV1/FVC post-bronchodilator, FEV1/FVC % of predicted normal value post-bronchodilator.

Separate summaries will be produced using the Safety, ITT and PP populations.

8.4.7 EXACT-PRO at Visit 1 Pre-dose

The EXACT-PRO total score and domain scores at Visit 1 (pre-dose) will be summarised by treatment regimen and overall using the ITT and PP populations.

8.4.8 CRQ at Visit 1 Pre-dose

The CRQ total score and domain scores at Visit 1 (pre-dose) will be summarised by treatment regimen and overall using the ITT and PP populations.

8.4.9 BODE index at Visit 1 Pre-dose

For the subgroup of patients enrolled in the study under protocols V2.0 and V3.0, the BODE index and subscores at Visit 1 (pre-dose) will be summarised by treatment regimen and overall using the ITT and PP populations.

8.4.10 Other Baseline and disease characteristics

Gynaecological history data will be summarised by treatment regimen and overall using the ITT population and listed. Additional investigations performed for COPD exacerbation data (microbiology culture, arterial blood gases, chest X-ray, chest CT scan, other) will be summarised by treatment regimen and overall using the ITT and PP populations and listed. Other Baseline and disease characteristics data will be listed.

8.4.11 Medical history and concomitant diseases

A summary of medical history and concomitant diseases will be presented by system organ class (SOC) and preferred term (PT), by treatment regimen and overall using Medical Dictionary for Regulatory Affairs® (MedDRA) Version 20.0 or higher. Separate summaries will be produced using the Safety and ITT populations. A listing of medical history and concomitant diseases will be provided.

Note:

- Medical histories are defined as records in the medical history and concomitant diseases eCRF form which are not ongoing at Screening Visit
- Concomitant diseases are defined as records in the medical history and concomitant diseases eCRF form which are ongoing at Screening Visit.

8.4.12 Prior and concomitant medications

Prior and concomitant medications will be coded using the World Health Organization (WHO) Drug Dictionary (March 2017 or later).

Prior and concomitant medications will be summarised by ATC classification and Preferred Name by treatment regimen for the ITT population through frequency distributions and percentages and presented in separate tables for the following groups:

- Previous medication (discontinued prior to study treatment):
 - COPD medications.
- Medication concomitant to study treatment:
 - COPD medications not including medications for COPD exacerbation
 - Medications for COPD exacerbation
 - Non-COPD medications.
- Medications occurring in the Stabilisation Phase (post-treatment medication):
 - Medications for COPD exacerbation.

The following rules to identify COPD medications (administered for COPD exacerbations and for other reasons) are proposed for selecting medications:

COPD medications:

Any medications with an indication = ‘COPD exacerbation: current/during the study’ or ‘COPD (non-exacerbation related)’ or ‘Rescue medication’, or which contains ‘COPD’ or ‘CHRONIC OBSTRUCTIVE PULMONARY DISEASE’ or ‘RESCUE MEDICATION’ for ‘Indication, specify’ field will be considered as COPD medications.

Medications for COPD exacerbations:

Any medications with an indication = ‘COPD exacerbation: current/during the study’ will be considered as medications for COPD exacerbations.

Details for imputing missing or partial start and/or stop dates of medication are described in Section 7.2.2.3.

8.4.13 Vital signs at Screening and Visit 1 Pre-dose

Body temperature, systolic (SBP) and diastolic (DBP) blood pressure, pulse rate (PR), respiratory rate (RR), blood oxygen (% HbO₂ saturation) assessed pre-salbutamol at Screening and pre-dose at Visit 1 will be summarised by treatment regimen and overall using the Safety population.

8.4.14 12-lead ECG at Screening and Visit 1 Pre-dose

The HR, RR, PR, QRS, QT, QTcB and QTcF values obtained from the 12-lead ECG pre-salbutamol at Screening and pre-dose at Visit 1 will be summarised by treatment regimen and overall using the Safety population.

8.4.15 Eosinophils at Screening and Visit 1 Pre-dose

Descriptive summaries of eosinophils relative count (%) collected at Screening and pre-dose at Visit 1 will be presented. A summary for eosinophils (%) (<2% or ≥2%) will also be presented. All summaries will be by treatment regimen and overall using the ITT and PP populations.

8.5 Extent of exposure

8.5.1 Treatment duration

Exposure to randomised IMP (number of days) will be defined as:

(date of last dose of randomised IMP – date of first dose of randomised IMP) + 1

and

8.5.2 Treatment compliance

IMP administration details, including the number of capsules administered and the complete/partial administration of study drug dose (and reason, if partial) [REDACTED] by treatment regimen on the ITT population using descriptive statistics.

The total number of doses taken as well as the overall treatment compliance (%) will also be presented by treatment regimen using the ITT population.

The formula for overall compliance (%) calculation is:

Compliance (%) = (total number of capsules administered / 6)*100

8.6 Efficacy analyses

This section addresses separately the analyses to be conducted on the primary, secondary and exploratory efficacy variables.

All definitions relative to efficacy and exploratory endpoints are detailed in Section 7.1.4.

8.6.1 Analysis methods

Descriptive statistics will be presented for all endpoints. All statistical tests of the efficacy and exploratory endpoints will be two-sided tests and compared to a 5% significance level and all estimates will be presented with two-sided 95% CIs, unless otherwise specified.

Unless otherwise stated, all ANCOVA models and repeated measures models will include the baseline value (last non-missing value collected prior to the first dose of study medication) of the variable as covariate and treatment regimen, severity of airflow limitation at baseline (post-bronchodilator FEV1 at baseline (pre-dose) <30% or ≥30% of predicted normal value), blood eosinophils (%) value at baseline (<2% or ≥2%), time from start of current COPD exacerbation to first IMP dosing (≤2 days, 3-4 days or ≥5 days), presence of cardiovascular comorbidities at screening (yes, no) and COPD exacerbation treatment at screening (systemic corticosteroids only, antibiotics only or both systemic corticosteroids and antibiotics) as fixed effects. Repeated measures models will also include visit/inter-visit period, the treatment by visit/inter-visit period interaction and the baseline by visit/inter-visit period interaction. The adjusted mean difference between treatment regimens will be presented along with a two-sided 95% CI for the time-points of interest.

The calculation of the adjusted means (least squares means) will be based on:

- coefficients for classification effects (i.e., the effects of categorical covariates) proportional to the margins observed in the group of patients analysed;
- effects of quantitative covariates set equal to their mean values in the group of patients analysed.

See Appendix F for details on the calculation of adjusted means (least squares means).

8.6.1.1 Multiplicity

All three treatment regimens will be assessed by pairwise comparisons. No adjustment will be made for multiple comparisons.

8.6.1.2 Treatment by center interaction analysis (multi-center study)

No analysis will be made to assess the treatment-by-center interaction.

8.6.2 Analysis of primary efficacy endpoint(s)

The primary efficacy endpoint for this study is the change in FEV1 from baseline (pre-dose) to Day 7, defined as: FEV1 value at Day 7 – FEV1 value at baseline (pre-dose).

8.6.2.1 Primary analysis

The primary analysis of efficacy will be based on the ITT population and observed cases.

The primary analysis will compare each of the treatment regimens together using pairwise comparison tests based on a mixed model for repeated measurements (MMRM) using an unstructured covariance matrix and the Kenward-Roger adjustment for the denominator degrees of freedom. The model will use FEV1 absolute changes at Days 2, 3, 4, 5, 6 and 7, and will include treatment [REDACTED] severity of airflow limitation at baseline (post-bronchodilator FEV1 at baseline (pre-dose) <30% or ≥30% of predicted normal value), blood eosinophils (%) value at baseline (<2% or ≥2%), time from start of current COPD exacerbation to first IMP dosing (≤2 days, 3-4 days or ≥5 days), presence of cardiovascular comorbidities at screening (yes, no) and COPD exacerbation treatment at screening (systemic corticosteroids only, antibiotics only or both systemic corticosteroids and antibiotics) as fixed effects and baseline FEV1 value as covariate. In addition the baseline FEV1 value-by-visit and the treatment-by-visit interactions will be included in the model.

LSMEAN and standard error (SE) of each treatment regimen as well as the adjusted mean difference between treatment regimens and associated two-sided 95% CIs will be obtained from the MMRM model at Days 2, 3, 4, 5, 6 and 7. Each pairwise treatment regimen comparison will be tested at an alpha level of 5%. Difference will be considered and confirmed between pairwise treatments if the two-sided P-value for the test for difference is below 0.05. P-values of the effects will also be presented.

Hypotheses:

The 'superiority' null hypothesis will be:

$H_0: T2-T1 = 0$ (T2 is equivalent to T1) vs the alternative

$H_a: T2-T1 \neq 0$ (T2 is different to T1)

MMRM model and SAS code:

The SAS code used to implement linear mixed model for repeated measures for FEV1 and 95% CIs of differences between treatments will be similar to that shown below:

PROC MIXED data = dataset;

CLASS ID trt visit severity eosino time_symp cv_comorb COPD_trt;

*MODEL change = trt visit trt*visit severity eosino time_symp cv_comorb COPD_trt baseline*

*baseline*visit / ddfm=KenwardRoger;*

REPEATED visit / subject=ID type=UN;

*LSMEANS trt*visit / cl;*

LSMEANS trt / cl;

*LSMESTIMATE trt*visit*

'A vs B: Visit 2' 1 0 0 0 0 0 -1 0 0 0 0 0 0 0 0 0 0 0,

'A vs B: Visit 3' 0 1 0 0 0 0 0 -1 0 0 0 0 0 0 0 0 0 0,

'A vs B: Visit 4' 0 0 1 0 0 0 0 0 -1 0 0 0 0 0 0 0 0 0,

'A vs B: Visit 5' 0 0 0 1 0 0 0 0 0 -1 0 0 0 0 0 0 0 0,

'A vs B: Visit 6' 0 0 0 0 1 0 0 0 0 0 -1 0 0 0 0 0 0 0,

'A vs B: Visit 7' 0 0 0 0 0 1 0 0 0 0 0 -1 0 0 0 0 0 0,

'A vs C: Visit 2' 1 0 0 0 0 0 0 0 0 0 0 0 -1 0 0 0 0 0,

'A vs C: Visit 3' 0 1 0 0 0 0 0 0 0 0 0 0 0 0 -1 0 0 0 0,

'A vs C: Visit 4' 0 0 1 0 0 0 0 0 0 0 0 0 0 0 0 -1 0 0 0,

'A vs C: Visit 5' 0 0 0 1 0 0 0 0 0 0 0 0 0 0 0 0 -1 0 0,

'A vs C: Visit 6' 0 0 0 0 1 0 0 0 0 0 0 0 0 0 0 0 -1 0,

'A vs C: Visit 7' 0 0 0 0 0 1 0 0 0 0 0 0 0 0 0 0 0 -1,

'B vs C: Visit 2' 0 0 0 0 0 0 1 0 0 0 0 0 0 -1 0 0 0 0 0,

'B vs C: Visit 3' 0 0 0 0 0 0 0 1 0 0 0 0 0 0 -1 0 0 0 0,

'B vs C: Visit 4' 0 0 0 0 0 0 0 0 1 0 0 0 0 0 0 -1 0 0 0,

'B vs C: Visit 5' 0 0 0 0 0 0 0 0 0 1 0 0 0 0 0 0 -1 0 0,

'B vs C: Visit 6' 0 0 0 0 0 0 0 0 0 0 1 0 0 0 0 0 0 -1 0,

'B vs C: Visit 7' 0 0 0 0 0 0 0 0 0 0 0 1 0 0 0 0 0 0 -1 / cl;

LSMESTIMATE trt;

'A vs B: Overall' 1 -1 0,

'A vs C: Overall' 1 0 -1,

'B vs C: Overall' 0 1 -1 / cl;

RUN;

Notes:

- Change represents the change from baseline to each visit of the variable;
- Trt represents the treatment group;
- Visit represents the clinic visit;
- Severity represents the severity of airflow limitation (post-bronchodilator FEV1 at baseline (pre-dose) classified into 2 groups: < 30% or \geq 30% of predicted normal value);
- Eosino represents the blood eosinophils (%) value at baseline (classified into 2 groups: < 2% or \geq 2%);
- Time_symp represents the time from start of current COPD exacerbation symptoms to first IMP dosing (\leq 2 days, 3-4 days or \geq 5 days);
- Cv_comorb represents the cardiovascular comorbidities at screening (presence or absence);
- COPD_trt represents the COPD exacerbation treatment at screening (systemic corticosteroids only, antibiotics only or both systemic corticosteroids and antibiotics);
- Baseline represents the baseline value of the variable;
- ID represents the Patient Number;
- Treatment order: 1 = High dose BCT197, 2 = Low dose BCT197; 3 = Placebo
- the ‘Overall’ least squares means and contrasts will be estimated only for the change from baseline in FEV1.

In case of non-convergence of the above model using an unstructured covariance matrix, the following variance structures will be tested, and based on Akaike’s information criteria the best fitting model will be chosen. The variance models that will be considered for the within patient variation in case of non-convergence are in this order: Ante-dependence, Toeplitz, Heterogeneous AR(1), Heterogeneous Compound Symmetry, and Compound Symmetry.

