8.6.2.3 Sensitivity analyses

MMRM on PP Population:

Additionally to assess the robustness of the ITT results, a supportive MMRM analysis using the PP population will be carried out.

ANCOVA (OC):

The primary endpoint will be analysed using an ANCOVA model estimating the effect at Day 7, using OC, including treatment, severity of airflow limitation at baseline, blood eosinophils (%) value at baseline, time from start of current COPD exacerbation to first IMP dosing, presence of cardiovascular comorbidities at screening and COPD exacerbation treatment at screening as fixed effects and baseline FEV1 value as a covariate.

The ANCOVA model results will be presented with LSMEAN and standard error (SE) of each treatment regimen as well as the adjusted mean difference between treatment regimens at Day 7 and associated two-sided 95% CIs. Each pairwise treatment regimen comparison will be tested at an alpha level of 5%. Difference will be considered and confirmed between pairwise treatments if the two-sided P-value for the test for difference is below 0.05. P-values of the effects will also be presented.

ANCOVA Model and SAS code:

The SAS code used to implement ANCOVA model for FEV1 at Day 7 and 95% CIs of differences between treatments will be similar to that shown below:

```
PROC MIXED data = dataset;
  CLASS trt severity eosino time_symp cv_comorb COPD_trt;
  MODEL change_d7 = trt severity eosino time_symp cv_comorb COPD_trt baseline /
    ddfm=KenwardRoger;
  LSMEANS trt / cl;
  LSMESTIMATE trt;
    'A vs B: Overall'1 -1 0,
    'A vs C: Overall'1 0 -1,
    'B vs C: Overall'0 1 -1 / cl;
RUN;
```

Notes:

- Change_d7 represents the change from baseline to Day 7 of the variable;
- Trt represents the treatment group;
- Severity represents the severity of airflow limitation (post-bronchodilator FEV1 at baseline (pre-dose) classified into 2 groups: < 30% or ≥ 30% of predicted normal value);
- Eosino represents the blood eosinophils (%) value at baseline (classified into 2 groups: < 2% or ≥ 2%);
- Time_symp represents the time from start of current COPD exacerbation symptoms to first IMP dosin [REDACTED];

-
- Cv_comorb represents the cardiovascular comorbidities at screening (presence or absence);
 - COPD_trt represents the COPD exacerbation treatment at screening (systemic corticosteroids only, antibiotics only or both systemic corticosteroids and antibiotics);
 - Baseline represents the baseline value of the variable;
 - Treatment order [REDACTED]

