 - the ‘Overall’ least squares means and contrasts will be estimated only for the change from baseline in FEV1.

MMRM on subgroup of patients enrolled in the study under protocols V4.0 and V5.0:

For patients enrolled in the study under protocols V4.0 and V5.0, the inclusion criterion 7 regarding post-bronchodilator spirometry was removed, as it was challenging in the acute exacerbation setting to conduct pre- and post- bronchodilator spirometry. Thus, all spirometry measurements were performed ‘on bronchodilator’ for patients enrolled in the study under protocols V4.0 and V5.0 (i.e. the way of measuring the primary efficacy endpoint has been changed).

Therefore, a MMRM analysis using the ITT population will be performed as a sensitivity analysis on the subgroup of patients enrolled in the study under protocols V4.0 and V5.0.

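### Nine of the 12 placebo contrasts in the sample MMRM code carry a surplus zero, so the low dose vs placebo row at Day 7 contains no placebo term

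*SAP*

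**What the plan says.** SAP section 8.6.2.1 models change in FEV1 at Days 2 to 7 in three regimens. The prose asks that "the adjusted mean difference between treatment regimens and associated two-sided 95% CIs will be obtained from the MMRM model" at each of those days, with every pairwise comparison tested at the two-sided 5% level. The code is introduced with the words "for FEV1 and 95% CIs of differences between treatments will be similar to that shown below". Its notes fix the order of the arms: "Treatment order: 1 = High dose BCT197, 2 = Low dose BCT197; 3 = Placebo". The code calls these A, B and C.

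Treatment differences are requested through `LSMESTIMATE` rows on `trt*visit`. Two rows show the problem. The high dose vs placebo row for Visit 3 reads "0 1 0 0 0 0 0 0 0 0 0 0 0 0 -1 0 0 0 0", and the low dose vs placebo row for Visit 7 reads "0 0 0 0 0 0 0 0 0 0 0 1 0 0 0 0 0 0 -1 / cl".

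Section 8.6.2.3 adds a Day 7 ANCOVA with its own code, and two further repeated-measures analyses without separate code: "a supportive MMRM analysis using the PP population will be carried out", and "a MMRM analysis using the ITT population will be performed as a sensitivity analysis on the subgroup of patients" enrolled under protocol versions 4.0 and 5.0.

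**The concern.** A contrast row must have as many coefficients as the effect has cells, with each coefficient in the cell that its label names. Several placebo rows are one coefficient too long, which moves the placebo -1 away from the visit on the label.

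Low dose vs placebo at Day 7 is one of the two placebo comparisons on the primary endpoint. The printed `LSMEANS` statements ask only for confidence limits, and Appendix F adds weighting options but no differences. The `LSMESTIMATE` rows are therefore the only place where the printed code produces treatment differences from the MMRM. No other MMRM code is printed for the per-protocol or version 4.0/5.0 analyses of FEV1, so a programmer working from the SAP could carry the slip into those as well.

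**Working it through.** **Inputs.** Three regimens in the order A, B, C (notes to the code, 8.6.2.1). Six visits, Days 2 to 7 (8.6.2.1; the Appendix F example likewise drops Visit 1 and keeps Visits 2 to 7). Visit 7 is Day 7: Appendix B lists the mMRC at visits 1, 7, 9, 10, 11 and 12, which matches its collection at Baseline, Day 7, Day 14 and Weeks 8, 12 and 26 in the schedule.

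**Cell layout.** 3 × 6 = 18 cells. The `CLASS` statement lists treatment before visit, so visit varies fastest: A is in cells 1–6, B in 7–12, C in 13–18. The placebo cell for visit v is 12 + (v − 1). A valid row has 18 coefficients, with the -1 standing 6 places after the +1 (A vs B, B vs C) or 12 places after it (A vs C).

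**Counting the printed rows.**

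| Rows | Coefficients | +1 at | -1 printed at | -1 belongs at |
|---|---|---|---|---|
| A vs B, Visits 2–7 | 18 | 1–6 | 7–12 | 7–12 |
| A vs C, Visits 2, 6, 7 | 18 | 1, 5, 6 | 13, 17, 18 | 13, 17, 18 |
| A vs C, Visits 3, 4, 5 | 19 | 2, 3, 4 | 15, 16, 17 | 14, 15, 16 |
| B vs C, Visits 2–6 | 19 | 7–11 | 14–18 | 13–17 |
| B vs C, Visit 7 | 19 | 12 | 19 | 18 |

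Nine rows are right and nine are wrong. In each wrong row there is one extra zero between the +1 and the -1 (12 instead of 11 for A vs C, 6 instead of 5 for B vs C), while the leading and trailing zeros fit the label. The code also contradicts itself: A vs C at Visit 5 and at Visit 6 both place the -1 in cell 17, so one placebo cell serves two different days.

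**Day 7, low dose vs placebo.** The first 18 coefficients sum to +1, not 0. Within the model's cells the row is the low-dose Day 7 mean and not a contrast.

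**Stray semicolon.** In the MMRM code (overall contrasts) and in the Day 7 ANCOVA code, a semicolon follows "LSMESTIMATE trt" and ends the statement before its contrast lines.

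**The plan's sample size, for reference.** SAP section 5 gives 100 mL, SD 230 mL, two-sided 5% and 80% power: 2 × (1.960 + 0.842)² × 230² / 100² = 83.04, rounded up to 84 per arm against 85 stated. It reproduces and is not affected.

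**Illustration of size.** This assumes that the software ignores coefficient 19, that the drug has no effect, and SD 230 mL with 85 per arm.

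- SE of one arm's mean = 230/√85 = 24.9 mL. SE of a difference = 230 × √(2/85) = 35.3 mL.
- If every arm gains 25, 50 or 100 mL by Day 7 on standard of care (assumed), the printed row tests a mean that lies 1.0, 2.0 or 4.0 SEs from zero. With a two-sided noncentral t on 252 degrees of freedom, p < 0.05 occurs in about 17%, 51% or 98% of trials instead of 5%.
- If the software instead rejects the row, there is no estimate and no bias.
- If the eight shifted rows run as printed, each is off by one day of placebo recovery: −10 to −40 mL if placebo gains 10 to 40 mL per day (assumed).

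**The case against.** The strongest reply is that the code is a sample. The SAP says the final program will be similar, and Appendix F already requires options that the printed `LSMEANS` lines lack, so the final program had to differ. The governing prose states the comparisons correctly. This stands, and it is why the point concerns the code and not the method.

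Second, the text was read from a PDF, and a long run of zeros is an easy place to duplicate a character. This cannot be excluded without the original page. But the same single extra zero, always between the +1 and the -1, in all six B vs C rows looks more like copied drafting than random damage.

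Third, the documents do not say how the software treats a surplus coefficient, so both the wrong-day comparisons and the rejection rates above are conditional. That is also true.

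Fourth, the error might be caught: the arm means are printed, and (A − C) − (A − B) recovers the B − C point estimate at Day 7, though not its confidence interval or p-value. The semicolon would probably show up when the code is run. These points lower the chance that a wrong result is reported. They do not make the printed rows right, and the eight shifted rows still sum to zero, so a wrong-day comparison would look plausible in the output.

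**Conclusion.** The concern holds, with high confidence in the count. Nine of the 12 placebo rows are wrong: all six for low dose vs placebo and three of six for high dose vs placebo. At Day 7 one of the three pairwise contrasts is wrong, namely low dose vs placebo; high dose vs placebo and high vs low dose are correct. As printed, neither the MMRM code nor the Day 7 ANCOVA code yields a valid low dose vs placebo difference at Day 7. The intended analysis is clear from the prose, and the model, hypotheses, populations and sample size are untouched. The conclusion assumes that the extracted text matches the original page. Any numerical distortion further depends on the software accepting 19 coefficients and on the code being followed as printed. This should be corrected, because these rows are the SAP's only printed specification of the MMRM treatment contrasts.

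**What to change.** 1. Check the original SAP page to rule out an extraction slip.
2. In the nine rows, delete one zero between the +1 and the -1, so that each row has 18 coefficients and the placebo -1 is in position 12 + (visit − 1). For low dose vs placebo at Visit 7, the +1 is in position 12 and the -1 in position 18.
3. Alternatively, drop the hand-typed vectors and request within-visit differences by option, for example a `SLICE` statement on `trt*visit` by visit with differences and confidence limits. That returns the 3 × 6 = 18 comparisons wanted, whereas asking for all differences on `trt*visit` returns 18 × 17 / 2 = 153 cell pairs.
4. Delete the semicolon after `LSMESTIMATE trt` in both the MMRM and the ANCOVA code, and use the corrected MMRM code for the per-protocol and version 4.0/5.0 analyses.

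The cost is a correction to the SAP's sample code. No new data are needed and the stated method does not change.
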